6.3 Protocol Deviations

Protocol deviations will be classified as minor or major deviations and reviewed at a data review meeting. Subjects with any major deviation that may impact the primary efficacy parameter will be excluded from the per-protocol analysis set, including the following:

- Violations inclusion and/or exclusion criteria (pre and/or intra-operative assessment)
- Use of prohibited medication known to influence the primary endpoint
- Randomization or treatment errors
- Improper administration of study product
- Improper assessment of the primary endpoint

7. STATISTICAL ANALYSIS

7.1 General

The analyses described in this SAP refer to Amendment 2 of the Clinical Investigation Plan (dated 2015 Nov 09). Unless otherwise noted, all analyses will be performed using [REDACTED].

Copyright© 2002-2012, [REDACTED] and all other [REDACTED] Inc. product or service names are registered trademarks or trademarks of [REDACTED], USA. All Rights Reserved. If not specified otherwise, data will be presented by planned [REDACTED]

[REDACTED]

treatment group and overall. Safety data will be summarized by actual treatment and overall. Continuous variables will be summarized by the following sample statistics: number of non-missing observations, mean, standard deviation (SD), median, minimum and maximum. Categorical variables will be presented by their absolute frequency and percentage (based on the number of subjects in the respective group).

7.2 Handling of Missing Data

Only subjects for whom endpoint data are available will be included in the statistical analysis. Missing values will be neither replaced nor estimated in the primary analysis.

7.3 Data Safety Monitoring Board

This study will be monitored by an independent unblinded DSMB. The DSMB will be composed of 3 members, 2 members who are recognized experts in the field of neurosurgery clinical care and research and 1 member who is a biostatistician. One (1) of the members shall serve as chairperson of the DSMB. The DSMB neurosurgeons will not be involved in enrolling or treating study subjects.

The DSMB will monitor ongoing safety data (AEs and laboratory test results). The DSMB will review safety and efficacy data from the study after 50% of the subjects have been completed, and will have the discretion to recommend stopping the trial due to safety, efficacy, or futility concerns. The stopping rules are presented in Section 7.4.

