4.4 Removal of Patients from Therapy, Assessment, or Study

Any patient may voluntarily withdraw (ie, reduce the degree of participation in the study) consent for continued participation and data collection. The reason for withdrawal will be recorded on the End of Study electronic case report form (eCRF). Assessments to be performed at the termination visit (including in cases of withdrawal or discontinuation) are described in [Section 6.16](#) and [Section 7.6](#).

Discontinuation (ie, complete withdrawal from study participation) may be due to drop out (ie, active discontinuation by patient) or loss to follow-up (ie, discontinuation by patient without notice or action). Additionally, the investigator and the sponsor have the discretion to discontinue any patient from the study if, in their judgment, continued participation would pose an unacceptable risk for the patient.

The data safety monitoring board (DSMB) will upgrade an AE to a serious adverse event (SAE) if the AE results in a patient injury that: jeopardizes the patient and may require medical or surgical intervention, prolongs the hospitalization, requires intervention to prevent permanent impairment or damage, causes disability or permanent damage, causes a congenital anomaly/birth defect, is life-threatening, or results in death.

The study enrolment will be paused and re-evaluated by the DSMB if:

- 2 or more SAEs occur in the same patient and are directly related to the investigational product, across 10 patients, or
- 20 aggregate SAEs occur that are directly related to the investigational product, or
- 1 patient death occurs that is directly related to administration of the investigational product.

The DSMB is required to define the rule(s) appropriate to restart the study, if the above triggering events occur during study conduct.

Discontinuation may also be due to the Institutional Review Board/Independent Ethics Committee (IRB/IEC) or Competent Authority's decision to terminate or suspend approval of the study or the investigator.

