9.2 Determination of Sample Size

This study is designed to show non-inferiority (NI) of FS VH S/D 500 s-apr compared to DuraSeal Dural Sealant based on the primary composite efficacy endpoint. The proportion of patients meeting the composite primary endpoint is assumed to be █% for FS VH S/D 500 s-apr and █% for DuraSeal. Using a non-inferiority margin of 10% (the largest clinically acceptable difference), a 1-sided Type 1 error rate (α) of 2.5%, a statistical power ($1-\beta$) of 80%, that one interim analysis is performed after 50% of the patients complete the study, the sample size estimation results in 202 evaluable patients. Assuming a group sequential design utilising O'Brien-Fleming boundaries, the study may be stopped early for futility if a p-value >0.2486 is observed at the interim. The estimation of sample size was performed using █ software (█, █).

The primary analysis will be performed on the per protocol set (PPS). Assuming that the PPS is 10% less than the total number of randomised patients, 112 patients per treatment group should be randomised, and there will be 224 patients in total.

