9.5 Interim Analysis

An interim analysis will be conducted after the completion of 50% of patients. A group sequential design utilising O'Brien-Fleming boundaries will be carried out. Basic demographic tables will be produced during the interim analysis. The study may be stopped early for futility if a p-value > 0.2486 is observed. If the study is stopped early, a full analysis of all of the data will be produced.

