10.10 Data Safety Monitoring Board

This study will be monitored by an independent unblinded DSMB. The DSMB will be composed of 3 members, 2 members who are recognized experts in the field of neurosurgery clinical care and research and 1 member who is a biostatistician. One (1) of the members shall serve as chairperson of the DSMB. The DSMB neurosurgeons will not be involved in enrolling or treating study patients.

The DSMB will monitor ongoing safety data (AEs and laboratory test results). The DSMB will review safety and efficacy data from the study after 50% of the patients have been completed, and will have the discretion to recommend stopping the trial due to safety, efficacy, or futility concerns. The rules to pause the study enrolment and re-evaluate the study are presented in Section [4.4](#).

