5.3 Sample Size

The number of subjects in a clinical trial should always be large enough to provide a reliable answer to the questions addressed. This number is usually determined by the primary objective of the trial. If the sample size is determined on some other basis, then this should be made clear and justified. For example, a trial sized on the basis of safety questions or requirements or important secondary objectives may need larger numbers of subjects than a trial sized on the basis of the primary efficacy question (see ICH E1A).

This study is designed to show non-inferiority (NI) of FS VH S/D 500 s-apr compared to DuraSeal Dural Sealant based on the primary composite efficacy endpoint. The

proportion of patients meeting the composite primary endpoint is assumed to be █% for FS VH S/D 500 s-apr and █% for DuraSeal. Using a non-inferiority margin of 10% (the largest clinically acceptable difference), a 1-sided Type 1 error rate (α) of 2.5%, a statistical power ($1-\beta$) of 80%, that one interim analysis is performed after 50% of the patients complete the study, the sample size estimation results in 202 evaluable patients. Assuming a group sequential design utilizing O'Brien-Fleming boundaries, the study may be stopped early for futility if a p-value >0.2486 is observed at the interim. The estimation of sample size was performed using SAS 9.4 software (SAS Institute; Cary, NC). The primary analysis will be performed on the per protocol analysis set (PPS). Assuming that the PPS is 10% less than the total number of randomized subjects, 112 patients per treatment group should be randomized, and there will be 224 patients in total.

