7.4 Interim Analysis

An interim analysis will be conducted after the completion of 50% of patients. A group sequential design utilizing O'Brien-Fleming boundaries will be carried out. Basic demographic tables will be produced during the interim analysis. Predicted values for the primary outcome will be produced from a logistic regression equation containing terms for treatment, site and surgical region (supratentorial or posterior fossa). A one-sided two sample t-test will be performed to compare the lower bound of the difference (active – control) between treatments in the mean predicted proportions against the null value of -0.1, to test whether the mean predicted value for Tisseel is less than -0.1 less than the mean predicted value for Duraseal. The study may be stopped early for futility if a p-value >0.2486 is observed. If the study is stopped early, a full analysis of all of the data will be produced.

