10. EFFICACY

10.1 Primary Efficacy Assessment

The primary efficacy analysis will be carried out on the PPS. The analysis using the FAS will be supportive. The primary efficacy endpoint is the proportion of patients who have neither of the following:

- Intra-operative CSF leakage from dural repair after up to two FS VH S/D 500 s-apr/control applications during Valsalva manoeuvre (25 cm H₂O for up to 5 - 10 seconds)
- Post-operative CSF leakage within 30 (+3) days post-operatively

The specific hypotheses of the proportion difference to be tested are as follows:

$$H_0: P_{FS} - P_{DS} \leq -0.10$$

$$H_a: P_{FS} - P_{DS} > -0.10$$

P_{FS} = the proportion of patients not meeting the 2 criteria (ie, no intra-operative CSF leakage and no post-operative CSF leakage) for the FS VH S/D 500 s-apr treatment group, and

P_{DS} = the proportion of patients not meeting the 2 criteria (ie, no intra-operative CSF leakage and no post-operative CSF leakage) for the DuraSeal Dural Sealant treatment group.

The primary composite efficacy endpoint, proportion of patients not meeting the 2 criteria (ie, no intra-operative CSF leakage and no post-operative CSF leakage), will be investigated by a 2-sided test for non-inferiority using logistic regression, taking into account the following covariates: study center and surgery region. The null hypothesis will be tested against the alternative using logistic regression, taking into account the following covariates: study center and surgery region (supratentorial or posterior fossa). The method described in reference 1 will be used: The parameters of the fitted logistic regression model will be used to predict the success rate of all subjects for both Tisseel and Duraseal treatment. The average response rate per group will be calculated as well as the difference between the two rates. The standard error of the difference will be derived using the delta method in order to construct a 95% confidence interval. A non-inferiority margin of 10% (the largest clinically acceptable difference) will be used; thus, if the lower bound of the 2 sided 95% CI (based on normal approximation) around the difference in proportions (Tisseel group – Duraseal group) is greater than -10% in the final analysis, Tisseel will be declared non-inferior to Duraseal.

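### The DSMB may recommend stopping for efficacy at the 50% look, but no efficacy boundary is stated, so the one-sided 2.5% is not guaranteed if an early stop leads to a non-inferiority claim

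*SAP*

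**What the plan says.** - **Stopping grounds.** Protocol 10.10 and SAP 7.3 both have the unblinded DSMB review safety and efficacy data at 50% completion. Protocol 10.10 says the board "will have the discretion to recommend stopping the trial due to safety, efficacy, or futility concerns". SAP 7.3 uses the same words and adds where the rules are to be found: "will have the discretion to recommend stopping the trial due to safety, efficacy, or futility concerns. The stopping rules are presented in Section 7.4".
- **Where the cross-references lead.** SAP 7.4 names O'Brien-Fleming boundaries but gives one rule: "The study may be stopped early for futility if a p-value >0.2486 is observed". Protocol 10.10 points to Protocol 4.4, whose list opens "The study enrolment will be paused and re-evaluated by the DSMB if" and contains only counts of related SAEs and a related death.
- **Other interim text.** Protocol 9.2 says "the study may be stopped early for futility if a p-value >0.2486 is observed at the interim". SAP 5.3 and Protocol 9.5 carry the same rule. None gives a critical value for efficacy, an alpha-spending function or an adjusted confidence level.
- **Error rate and success criterion.** SAP 5.3 sets "a 1-sided Type 1 error rate (α) of 2.5"%. SAP 10.1 declares success if the lower limit of the two-sided 95% interval "is greater than -10% in the final analysis, Tisseel will be declared non-inferior to Duraseal". SAP 7.4 adds that a trial stopped early receives a full analysis of its data.

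**The concern.** Efficacy is listed as a ground separate from futility, and SAP 7.3 promises a rule that SAP 7.4 does not contain. If the board stopped for efficacy and the sponsor then claimed non-inferiority, the claim would rest on about half the patients (101 of 202 evaluable, or 112 of 224 randomised) with no pre-specified threshold. Any threshold would be chosen after unblinded data had been seen. SAP 10.1 already uses the whole one-sided 2.5% at the end, so nothing is reserved for an early claim.

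**Working it through.** **Inputs.** One-sided alpha 0.025, 80% power and one interim at 50% come from SAP 5.3. The futility value p > 0.2486 comes from SAP 7.4. The final criterion, an unadjusted two-sided 95% interval (critical value 1.960), comes from SAP 10.1. I assume an information fraction of exactly 0.5 and normal test statistics, with positive Z favouring non-inferiority. At the margin, Z₁ and Z₂ are standard normal with correlation √0.5.

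**Step 1: which design gives 0.2486?** For a futility-only O'Brien-Fleming design with drift D and constant C, the bounds are f₁ = D√0.5 − C/√0.5 at the interim and c = D − C at the end. They are solved so that P(Z₁ > f₁, Z₂ > c) is 0.025 at the margin and 0.80 under drift D. The solution is D = 2.8673 and C = 0.9537, so f₁ = 0.679 and the interim p-value is 0.24865. The final critical value is c = 1.914 (p = 0.0278).

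| O'Brien-Fleming variant | Interim futility p |
|---|---|
| Futility only, binding | 0.24865 |
| Futility only, non-binding | 0.2384 |
| Efficacy and futility, binding | 0.2428 |
| Efficacy and futility, non-binding | 0.2335 |
| Error-spending versions | 0.288 to 0.297 |

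Only the first agrees with the stated 0.2486, to within the last printed digit (0.248654 truncates to 0.2486 but rounds to 0.2487). That design sets aside no alpha for early success. The sample size of 202 cannot separate the designs, because the test-arm rate is blacked out. With 90.6% for control and an assumed 92% for test, the total is 200.9 for futility only and 203.0 with both bounds.

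**Step 2: type I error with no efficacy stop.**
- Futility ignored: P(Z₂ > 1.960) = 0.0250.
- Futility always followed: P(Z₁ > 0.679, Z₂ > 1.960) = 0.0226.

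**Step 3: type I error with an efficacy stop at Z₁ ≥ e and the final test unchanged.**
- Futility ignored: P(Z₁ ≥ e) + 0.0250 − P(Z₁ ≥ e, Z₂ > 1.960).
- Futility followed: replace 0.0250 by 0.0226.

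For the O'Brien-Fleming bound, e = 2.797 (p = 0.00258): 0.00258 + 0.02500 − 0.00160 = 0.0260 with futility ignored, and 0.00258 + 0.02263 − 0.00160 = 0.0236 with it followed. For the 95% interval at both looks, e = 1.960: 0.0250 + 0.0250 − 0.0084 = 0.0416, and 0.0250 + 0.0226 − 0.0084 = 0.0392.

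| Interim efficacy threshold | Futility ignored | Futility followed |
|---|---|---|
| None | 2.50% | 2.26% |
| O'Brien-Fleming, p = 0.0026 | 2.60% | 2.36% |
| p = 0.005 | 2.73% | 2.49% |
| p = 0.01 | 3.04% | 2.81% |
| 95% interval, p = 0.025 | 4.16% | 3.92% |

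With futility always followed, the total reaches 2.5% at Z₁ = 2.565 (p = 0.0052), and only a looser threshold exceeds it. With futility ignored, any efficacy stop exceeds 2.5%. The futility rule is permissive, so the right-hand column cannot be relied on.

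**Step 4: a calibrated alternative.** A two-look O'Brien-Fleming efficacy boundary with non-binding futility is Z ≥ 2.797 at the interim and Z ≥ 1.977 at the end (p = 0.0240, a 95.2% two-sided interval). Its total is 0.0250.

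**The case against.** The strongest reply is that no written rule leads to an early claim. SAP 7.4 has only a futility rule, SAP 10.1 ties the declaration to the final analysis, and the board only recommends. The phrase about concerns may mean worry that the product performs badly, and stopping for that reason cannot create a false non-inferiority claim. The match of 0.2486 to a futility-only design suggests that no efficacy stop was planned and that the word is loose drafting. And if a threshold were needed, O'Brien-Fleming is the family already named, which limits the excess to 0.10 point, or removes it if futility is followed.

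Much of this stands. Type I error is controlled under the numeric rules as written, the poor-performance reading is possible, and 4.16% requires a rule that the documents do not state. It does not close the gap. Futility is already a separate ground, so on the benign reading *efficacy* adds little, and the text does not say which meaning applies. SAP 7.4 does not say whether the full analysis after an early stop counts as the final analysis, so an early claim is left open. Naming a boundary family without a direction or a value does not fix a threshold: the variants examined put the interim efficacy p-value anywhere from 0.0015 to 0.0031.

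**Conclusion.** The concern holds, as a conditional gap. Both documents grant an efficacy ground for stopping, neither cross-reference leads to an efficacy rule, and the final test uses all of the one-sided 2.5%. If an early efficacy stop supports a claim, the excess over 2.5% with futility ignored runs from 0.10 point (O'Brien-Fleming interim bound) to 1.66 points (95% interval at both looks). With futility always followed there is no excess for interim thresholds at or stricter than p = 0.0052. The figures assume exactly 50% information and a normal approximation, and do not depend on the blacked-out success rate. The text should be corrected before anyone sees unblinded interim data.

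**What to change.** **Preferred.** Delete *efficacy* from the stopping grounds in SAP 7.3 and Protocol 10.10, and state in SAP 7.4 and Protocol 9.5 that the interim is for futility only and cannot support a non-inferiority claim. This agrees with the design behind 0.2486 and keeps the final 95% interval valid, with type I error at most 2.50%. The cost is wording in the two documents and in any charter the board works under. Sample size and final test do not change.

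**If an efficacy stop is intended.** State the boundary in SAP 7.4 and Protocol 9.5 (interim Z ≥ 2.797, final Z ≥ 1.977) and change the interval in SAP 10.1 to 95.2%. The direct cost is a slightly wider final interval. The futility value and sample size should then be re-derived. With both bounds and non-binding futility, the futility p-value is 0.2335 and the inflation factor over a fixed design is 1.0909, against 1.0475 for the binding futility-only design.

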7.4 Interim Analysis

An interim analysis will be conducted after the completion of 50% of patients. A group sequential design utilizing O'Brien-Fleming boundaries will be carried out. Basic demographic tables will be produced during the interim analysis. Predicted values for the primary outcome will be produced from a logistic regression equation containing terms for treatment, site and surgical region (supratentorial or posterior fossa). A one-sided two sample t-test will be performed to compare the lower bound of the difference (active – control) between treatments in the mean predicted proportions against the null value of -0.1, to test whether the mean predicted value for Tisseel is less than -0.1 less than the mean predicted value for Duraseal. The study may be stopped early for futility if a p-value >0.2486 is observed. If the study is stopped early, a full analysis of all of the data will be produced.

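### The interim futility p-value comes from a t-test on model-predicted probabilities, whose standard error leaves out the outcome variance, so the 0.2486 boundary is applied to the wrong statistic

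*SAP*

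**What the plan says.** SAP 7.4 builds the interim test in three steps.

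- Model: "Predicted values for the primary outcome will be produced from a logistic regression equation containing terms for treatment, site and surgical region".
- Test: "A one-sided two sample t-test will be performed to compare the lower bound of the difference" in mean predicted proportions (active minus control) against -0.1. Its purpose is given as "to test whether the mean predicted value for Tisseel is less than -0.1 less than the mean predicted value for Duraseal".
- Rule: "The study may be stopped early for futility if a p-value >0.2486 is observed".

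SAP 5.3 gives the same threshold as part of an O'Brien-Fleming group sequential design with one look at 50%. Protocol 9.5 repeats the threshold but names no test statistic, so SAP 7.4 is the only definition of the interim p-value.

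For the final analysis, SAP 10.1 predicts every subject under both treatments, averages, and takes the difference. There, "The standard error of the difference will be derived using the delta method in order to construct a 95% confidence interval". SAP 7.4 does not refer to this.

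SAP 7.3 says of the DSMB review: "The stopping rules are presented in Section 7.4". The only other numerical triggers are the safety pauses in Protocol 4.4 ("The study enrolment will be paused and re-evaluated by the DSMB if").

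**The concern.** A two-sample t-test takes its SE from the spread of its inputs within each arm. Here the inputs are fitted probabilities. Two patients in the same arm, site and region have the same fitted value, whether or not either of them leaked. If site and region had no fitted effect, everyone in an arm would share one value and the SE would be zero at any sample size. Neither the binomial variance nor the uncertainty of the coefficients enters.

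The boundary was derived for a properly standardised Z. Dividing by too small an SE pushes p towards 0 when the observed difference is above -10 points and towards 1 when it is below. Results between the intended cut-off and -10 points, which should permit a futility stop, would then pass. The DSMB would also see a p-value that overstates the evidence, and SAP 7.3 lets it recommend stopping for efficacy as well as futility.

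**Working it through.** **Inputs from the documents.** One-sided alpha 2.5%, power 80%, one look at 50%, margin 10 points, 202 evaluable patients, 1:1 allocation, futility at p > 0.2486 (SAP 5.3, 5.4, 7.4). DuraSeal success rate 90.6% (Protocol 9.2.1).

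**Assumed.** The FS VH S/D 500 s-apr rate is redacted; 92.0% is back-solved from 202. The interim has 101 patients. Site numbers and covariate effects are not in the documents and are varied below.

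**1. The plan's boundary.** A two-look, futility-only O'Brien-Fleming design with information 0.5 and 1 was solved from the bivariate normal of (Z1, Z2), correlation √0.5.
- Binding: interim z = 0.6787, p = 0.24865, final critical value 1.914, drift 2.867, sample-size inflation 1.047.
- Non-binding: p = 0.2384.

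The stated 0.2486 therefore matches the binding version. Either way it is a boundary for Z = (difference + 0.10)/SE.

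**2. The plan's sample size.** n per arm = [0.920 × 0.080 + 0.906 × 0.094] × 2.867² / (0.10 + 0.014)² = 0.15876 × 8.221 / 0.012996 = 100.4, rounded up to 101, or 202 in total.

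**3. Intended behaviour.** P(stop) at a true difference of -10 points is Φ(0.679) = 75%. At 92.0% v 90.6% it is Φ(0.679 - 2.867 × √0.5) = Φ(-1.349) = 8.9%.

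**4. Size of the SE error.** The interim was simulated with 8, 12 or 20 equal sites, site SD 0 or 1 on the logit scale, and 25% posterior fossa with odds ratio 0.6, using 3,000 replicates per scenario. SAP 7.4 does not say whether each patient is predicted under the own arm only or under both, so both were run.

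| Quantity | Delta method | t-test, own arm | t-test, both arms |
|---|---|---|---|
| Median SE | 0.049–0.066 | 0.017–0.039 | 0.012–0.028 |
| Times below delta-method SE | – | 1.5–3.2 | 2.1–4.5 |
| P(stop), true difference -10 points | 70–74% | 58–64% | 54–59% |
| P(stop), 92.0% v 90.6% | 8–11% | 3–5% | 3–6% |

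The true SD of the estimated difference was 0.055–0.074. The delta method is therefore close (slightly low) and the t-test is far too small. Scenario by scenario, 7 to 18 fewer trials per 100 stop at the margin.

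A further simulation with 4, 8 or 15 sites, no true site effect and a region log-odds effect of 0 to 1 gave the same picture. The own-arm t-test SE was 20–47% of the delta-method SE, and stops at the margin fell from 71–76% to 56–65%. At a true difference of -10 points the t-test gave p < 0.025 in 18–34% of interims, against 3–4% for the delta method.

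**5. What 0.2486 becomes.** The cut-off on the correct Z scale is 0.679 divided by the SE ratio. A ratio of 1.5 gives z = 0.453, p = 0.33. A ratio of 4.5 gives z = 0.151, p = 0.44.

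**6. Worked example.** Take 42/50 v 46/51, a difference of 0.8400 - 0.9020 = -0.0620.
- Unadjusted SE = √(0.84 × 0.16/50 + 0.902 × 0.098/51) = 0.0665. Z = 0.0380/0.0665 = 0.572, p = 0.284: may stop.
- Own-arm t-test SE of 0.017 to 0.039: Z = 2.24 to 0.98, p = 0.01 to 0.16: continue.

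**7. Final error rates.** These come from the bivariate normal with a final critical value of 1.96, treating the interim stop as always followed.
- Correct interim: type I error 0.0226, power 79.0%.
- SE ratio 1.5 to 4.5: type I error 0.0237 to 0.0245, power 80.3% to 81.3%.

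**The case against.** SAP 7.4 writes no SE formula. The same sentence contains two other phrases that cannot be meant literally: a lower bound tested against -0.1, and the doubled less-than wording. If those are loose drafting, the t-test may be too, and a programmer might use the SAP 10.1 SE. The direction also depends on which phrase is taken literally. If the lower bound is read as the difference minus 1.96 correct SEs, the study stops when Z < 0.679 + 1.96 = 2.639. At the planned effect that is Φ(2.639 - 2.027) = 73% of trials, the opposite error. On the reading used above the harm is small, and correcting it costs about 1 to 2 points of power. The suggested correction also leaves open that 0.2486 is a binding value used with an optional stop and a 1.96 final rule, and that sites with no failures make site coefficients inestimable.

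What stands: the stop rates hold only for the t-test reading and the stated assumptions, and the limited harm is agreed. What does not: a two-sample t-test on predicted values fixes its own SE, and nothing in SAP 7.4 points to SAP 10.1. That the sentence can also be read in a way that reverses the effect is a further reason to rewrite it. The binding question and the sparse-site problem are separate; the latter affects the final model too.

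**Conclusion.** The point holds: SAP 7.4 is wrong as written. The null value of -0.1 and the threshold of 0.2486 are both right, and stopping on a large p fits the hypotheses in SAP 10.1. The fault is the statistic to which the threshold is applied.

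That the SE omits outcome variance follows from the construction and needs no simulation. Its size, 1.5 to 4.5 times below the delta-method SE in the main simulation, rests on the assumed site numbers, covariate effects and 92.0% test rate. The consequence is a weaker futility rule than the one designed, with more patients enrolled when the product is truly at the margin. Wrong stops at the planned effect also fall, type I error stays below 2.5%, the stop is optional and the final analysis is untouched. This makes it a should-fix point, not a threat to the trial's conclusion.

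**What to change.** Replace the t-test sentence in SAP 7.4 with:

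> The difference (FS VH S/D 500 s-apr minus DuraSeal) and its delta-method standard error will be obtained from the interim data as in Section 10.1. Z = (difference + 0.10)/SE, and the one-sided p = 1 - Φ(Z) tests H0: PFS - PDS ≤ -0.10 against Ha: PFS - PDS > -0.10. The study may be stopped for futility if p > 0.2486.

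Delete the lower-bound phrase and the doubled less-than phrase.

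The cost is SAP wording only. The final-analysis program is reused on the interim data, and the margin, threshold and sample size do not change.
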